During recruitment, research staff will inform the subject of the general nature of the study, their privacy rights, expectations for their participation, the voluntary nature of their participation, and that their participation can be withdrawn at any time. Participants will be assured that refusal to participate will not affect their care in any way. At all times, research staff will make explicit the voluntary nature of the subjects' participation as well as potential situations for breaking confidentiality. Recruitment procedures will be HIPAA compliant and have been IRB approved in past studies.

Referrals. All participants in the screening will receive a handout of mental health and violence prevention resources. If an adolescent screens positive for severe depressive symptoms at any time during the study, regardless of eligibility for the study, the RA will discuss the score with the family, notify the attending pediatric emergency physician, and offer to contact the adolescent's pediatrician.

If an adolescent discloses suicidality or if the patient's family so desires, the RA will alert the patient's clinician (if appropriate) who will immediately initiate a psychiatric evaluation in the ED, or will contact the patient and his/her parent if disclosure occurs outside of the ED. (See "Mandatory Reporting & Crisis Management," below). If a patient is deemed to need psychiatric hospitalization based on the screening, they will be withdrawn from the study.

Assessments and Remuneration. In **Aim 2**, participants will complete a baseline assessment, an 8-week follow-up assessment and interview; in **Aim 3**, participants will complete a baseline assessment, an 8-week interview and an 8-week and 16-week computerized follow-up assessment. Follow-up assessments will take place online, on the telephone, or in private rooms at the PI's departmental office (separate from the ED) where privacy and confidentiality can be maintained (i.e., making sure no one can overhear the conversation).

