Participant confidentiality will be breached only to protect the safety and welfare of research participants and only in accordance with state and federal law. The exceptions to confidentiality include if the adolescent reports suicidality, homicidal thoughts, or that he/she is the victim of child abuse or neglect. If the adolescent reports suicidality or homicidality, parents will be notified, and an emergency psychiatric evaluation for inpatient hospitalization will be facilitated with the Pediatric Emergency Psychiatric Service at Rhode Island Hospital. If necessary, authorities will be notified. If child abuse or neglect is reported, a report will immediately be filed with the Department of Children, Youth and Families. This exception to breaking confidentiality – the case where a participant reveals child abuse, suicidality, or homicidality – will be explained in detail to both participants and parents prior to completing the assent/consent.

Finally, information collected in this research study will not be available to clinicians, parents, or to other researchers. All data will be collected specifically for use on this project.

Risk 3) Emotional Discomfort

Of note, members of the proposed mentorship team have substantial prior clinical and research experience with high-risk populations as evidenced through their biographical sketches. [name] has extensive clinical and research experience developing interventions for depressed, suicidal, and alcohol-abusing adolescents. [name] has extensive clinical and research experience with adolescent violence and substance abuse prevention.

Parental distress: If parents report feelings of distress as a result of being notified that their child is eligible for this research project, clinical resources will be offered. These include referrals for mental health counseling and information about violence hotlines and local community organizations.

Assessments: The assessment instruments are commonly used in research and clinical practice. We will minimize distress by presenting questions/program techniques in a supportive manner, assuring participants that they may refuse to answer questions that make them uncomfortable, and reminding them that they may terminate the assessment and/or intervention at any time.

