Although there is extremely low risk of an adverse reaction to the screening survey or qualitative interviews (and, in fact, benefits to participation in similar research have been demonstrated),[151] all potential participants will be provided with a list of community resources at the same time that they are approached by the RA about participation in the study. To minimize negative consequences from the screening survey or semi-structured interviews, the RA will be trained to immediately terminate the assessment and alert the PI and the patient's clinician in the case that the subject demonstrates physical or psychological instability.

Additionally, on completion of baseline and follow-up assessments, the RA will be alerted by the computer if a participant has reported suicidality or severe depressive symptoms. The RA will contact [name] or [name] at that time, and the teen will be further evaluated for risk of harm to self or others. To the extent that the adolescent is determined to be a risk to himself/herself or others, the parent will be notified and a referral to an emergency evaluation with the Pediatric Emergency Psychiatric Service at Rhode Island Hospital will be made.

Regarding the text-messaging component of the study, text message assessments do NOT induce depression despite repeated assessments of negative mood.[152] Momentary assessments have also been shown to be acceptable, feasible, and appropriate when used to ask sensitive assessments (e.g., suicidality,

mood, alcohol and substance use, eating disorders, and violence) among a variety of populations, including school-age adolescents, schizophrenics, the homeless, drug addicts, recently hospitalized suicidal patients, and college students.[153-163]

Text-message Data: Participants and parents will be explicitly instructed during the consent process that no one will be monitoring text-message data in real time. In the case of a crisis situation, the adolescent should call the provided crisis hotline number or the PI's phone number rather than text the program. Nonetheless, some participants may misinterpret these guidelines. Hence, text-message data will be reviewed regularly by the PI and her mentorship team. The software will also be designed to send participants a message that directs them to a crisis phone number, if data that is not expected by the text-message algorithm is received.

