OF NOTE: This protocol mirrors that used by other text-message-based interventions for mental health and other potentially sensitive behaviors/disorders (e.g. [39, 104, 164-168]), including one that is currently ongoing with [name] and [name] at Brown University (for suicidal adolescents). Moreover, as the text messages include *no* PHI and *no* sensitive information regarding diagnoses, they easily meet or exceed HIPAA regulatory standards [169].

Ongoing Safeguards: Due to the association between violence and mental health sequelae, it is possible that some participants will experience psychiatric symptoms during the course of the program that may warrant mental health care. In order to minimize the risk of mental health deterioration, all subjects may receive mental health treatment at any time during the study. Clinical need will determine whether it is appropriate for the participant to continue in the study.

The PI's email and phone number, and a crisis hotline number, will be provided to every participant. The participant will be instructed to call the PI in case of any problems with the study, or if s/he has an immediate mental health crisis. S/he will be encouraged to call the crisis number, or 911, as well, if in need of immediate mental health services. The participant will also be provided with a wallet card explaining why she is responding to text messages, in case s/he is asked by a teacher or employer.

If a participant is identified as needing mental health treatment, the PI or her mentors will contact the participant individually for further assessment, and will notify the participants' parents of any clinical needs. Evaluation by the Pediatric Emergency Psychiatric Service at Rhode Island Hospital will be initiated on the PI's discretion at any sign of suicidality, homicidality, or child abuse. Suicidal or homicidal attempts or completions, and hospitalizations, will be monitored as serious adverse events, and will be reported our hospital's IRB according to our Data Safety & Monitoring Plan. If a patient is deemed to need psychiatric hospitalization based on the screening, they will be withdrawn from the study.

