As additional safeguards, **if a child reveals substantial mental health problems, such as suicidal ideation/attempts, homicidal ideation, or clinical deterioration, or if such problems are identified during the course of the study**, the child will be evaluated as soon as possible, by the PI, the primary mentor, and (if indicated) the on-call RIH psychiatric crisis team, to make a clinical determination about whether the child requires hospitalization or other clinical services. The primary mentor is a licensed child clinical psychologist and has training and experience in intervening in similar crisis situations. Project staff will carry cell phones with them during all participant contact and will be instructed to contact the PI (who is on call and always carries a phone) immediately to inform her of any clinical emergency. Additionally, [name] and [name] will carefully monitor the symptom progression of all participants. **If a patient is deemed to need psychiatric hospitalization based on the screening, they will be withdrawn from the study.**

If any mental health problems are reported or identified at the time of the follow-up and the family is not in treatment, appropriate referral for psychological intervention will be arranged.

Whenever possible, study staff will handle these situations therapeutically. For example, if time limits and safety concerns allow, parents will be informed in advance and provided the opportunity to participate in the mandated report process. Research staff will contact the PI who will be responsible for any on-site clinical decision-making.

Over the past 10 years, in several ED studies conducted by myself and my mentors, staff have encountered only 2 cases of harm to others that involved crisis management procedures leading to breaching confidentiality and involving authorities, less than 10 cases of child abuse requiring mandatory reporting to the police, and regular suicide risk assessments (~10 participants per study, per month).

14c. Potential benefits of the proposed research to the subjects and others:

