Participation in this project could potentially benefit participants in a few important ways. The instruments used to obtain information in this study are commonly used in clinical and research practice but may invoke some emotional discomfort. Efforts will be made to minimize this discomfort by presenting questions in a supportive manner, assuring participants that they may refuse to answer questions that make them uncomfortable, and may terminate participation in the study at any time. It is also possible that the questions or assessments themselves may be beneficial to all participants by asking them to review their affect and peer violence. The screening and baseline assessments may therefore act as a very minimal intervention (as could any study with interviews regarding risky behaviors). Indeed, study participants in [name] and [name] previous, similar studies have commented that they have found the questions to be helpful.

Additionally, we hope that our intervention will be successful in preventing/reducing depressive symptoms, and possibly peer violence, in our subject population. The intervention offers the possibility of a relatively low-resource, highly-disseminable preventive intervention for a needy population. We therefore think that the clear examination of these questions outweighs the previously mentioned risks.

Because all youth participating in the study self-report depressive symptoms and peer violence, we felt it was necessary to enhance usual care (typically no violence-prevention or mental health information is routinely provided during the ED visit) for all youth. Thus, all youth participating in screening will review a health information brochure, with referral information for mental health problems including suicide hotlines, substance

use, and violence prevention and treatment services, anger management, etc. This pamphlet will be similar in style and content to that used in my mentors' prior work. In addition, as described above, participants that meet criteria for severe depressive symptoms or suicidality on the screening survey will be offered a clinical assessment and individualized referral in the ED, which exceeds the current standard of care.

In sum, potential benefits for the research far outweigh the risks for the participants. The proposed research also has significant benefits for society in general, as described in **Importance of the Knowledge to be Gained** (14d, below).

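### For a participant who reports suicidality and is then judged not at risk, section 14b.2 both requires and does not require parent notification and emergency evaluation

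*Combined protocol and SAP*

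**What the plan says.** All of the following is in section 14 of the combined protocol and SAP unless stated otherwise.

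- **14b.2, Risk 2 (Confidentiality).** The report is the trigger and no step comes between it and the response: "If the adolescent reports suicidality or homicidality, parents will be notified, and an emergency psychiatric evaluation for inpatient hospitalization will be facilitated". The same paragraph says that this exception to confidentiality will be explained to participants and parents before assent and consent.
- **14b.1, Referrals.** For a disclosure of suicidality in the ED, the research assistant alerts the clinician, with the qualifier that this is done if appropriate, "who will immediately initiate a psychiatric evaluation in the ED". Otherwise the text says staff "will contact the patient and his/her parent if disclosure occurs outside of the ED". No risk threshold is attached to that contact.
- **14b.2, Risk 3 (Assessments).** When a participant finishes a baseline or follow-up questionnaire, the trigger is again a report: "the RA will be alerted by the computer if a participant has reported suicidality or severe depressive symptoms". The teen is then evaluated further, and the consequences depend on the result: "To the extent that the adolescent is determined to be a risk to himself/herself or others, the parent will be notified". Referral for emergency evaluation is subject to the same condition.
- **14b.2, Risk 3 (Ongoing Safeguards).** Evaluation by the same hospital psychiatric service is started at the PI's "discretion at any sign of suicidality, homicidality, or child abuse".
- **14b.2, Risk 5.** For ideation revealed or identified during the study, the PI and the primary mentor evaluate, and the psychiatric crisis team joins only if indicated.
- **14f.** For significant suicidal risks, a term left undefined, parents are notified as 14b.2 describes and a crisis-team evaluation starts at once.
- **14c.** Participants with suicidality on the screening survey "will be offered a clinical assessment and individualized referral in the ED".

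Two operating documents are mentioned but not reproduced: a drafted crisis plan (Research Strategy, Mental Health Safeguards and Data Management) and a written protocol for reporting incidents (14b.2, Risk 5).

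**The concern.** Risk 2 and Risk 3 start from the same event, a teen reporting suicidality, and attach different consequences to it. Under Risk 2 the report is enough. Under Risk 3 the report leads to an assessment, and only a positive assessment leads to the parent and the emergency service. Staff who receive the alert cannot tell from the protocol whether a parent must be told when the assessment is reassuring.

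Two things are at stake. The first is the safety of minors who were selected for depressive symptoms: two teens who give the same answer and have the same assessment can be handled differently, according to which paragraph a staff member has in mind. The second is the promise made to families. Risk 2 is the rule that they are to be told before they agree. If staff follow Risk 3, a parent who was told to expect notification on any report may not receive it. If staff follow Risk 2, confidentiality is broken for a teen for whom Risk 3 would not require it. In either case, what was explained and what is done can part company.

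**Working it through.** No arithmetic applies: the point depends on no rate, power or sample size. The check is to see whether the provisions cover the same case and then to follow that case through each of them.

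**Step 1: do the provisions overlap?** Risk 2 is general and names no setting or time. Risk 3 (Assessments) covers reports at baseline and follow-up assessments. Ongoing Safeguards covers any sign during the program. Section 14b.1 (Assessments and Remuneration) places follow-up assessments online, by telephone or in the PI's departmental office, so a follow-up report also falls under the outside-the-ED clause of 14b.1 Referrals. A report on the 8-week survey meets all of these.

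**Step 2: a teen who reports suicidality at 8 weeks and is judged at risk.** Risk 2 and Risk 3 agree: the parent is notified and emergency evaluation is arranged. Only the discretion in Ongoing Safeguards differs.

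**Step 3: a teen who gives the same report and is judged not at risk.**

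| Provision | Parent | Emergency evaluation |
|---|---|---|
| 14b.2 Risk 2 | Notified | Facilitated |
| 14b.1 Referrals, outside the ED | Contacted | Not addressed |
| 14b.2 Risk 3, Assessments | Notification not required | Referral not required |
| 14b.2 Risk 3, Ongoing Safeguards | Told of clinical needs if treatment is found to be needed | At the PI's discretion |
| 14b.2 Risk 5 | Not addressed for this case | Crisis team only if indicated |
| 14f | Notified if the risk is significant | Immediate if the risk is significant |

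The first and third rows cannot both describe the plan for this teen. On the parent, 14b.1 sides with Risk 2.

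**Step 4: is there a rule of precedence?** None is stated. Section 14f refers back to 14b.2, which contains the conflict. Risk 5 introduces the written reporting protocol as following what is described above, and so also points back to the conflicting text. Risk 2 limits breaches of confidentiality to those that protect safety and welfare, so it cannot simply be assumed that staff will always take the broader disclosure.

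**Step 5: which version reaches families?** Risk 2 says that its own exception is the one to be explained. Risk 5 likewise says that the consent and assent forms will list suicidality among the occasions for breaking confidentiality, without mentioning a prior risk determination.

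**The case against.** The strongest reply is that much of this text describes one sensible sequence. Risk 3 (Assessments), Ongoing Safeguards and Risk 5 can be read together as alert, assessment by the PI or a mentor, then referral if indicated. On that reading there are two wordings rather than three rules, and clinical judgment in the middle is normal. This stands, and it narrows the point. It does not reach Risk 2, which has no assessment step, or the parent contact in 14b.1.

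It may also be said that the crisis plan or the written reporting protocol settles the matter. Either might. Their content is not in the documents, so they are a reason to check and not a reason to close the point. The consent pages are likewise not available, so no claim is made about what the forms actually say.

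A reader might infer more than the text supports:

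- *That the screening rules also conflict.* Eligibility and Enrollment (attending notified), 14b.1 Referrals (clinician evaluates) and 14a.1 (hospitalization decided on clinician assessment after notification of a positive screen) form a sequence. The wording in 14c is a looser summary and only needs aligning.
- *That the decision-maker changes from paragraph to paragraph.* The contacts in Risk 3 (Assessments) are removed names and may include the PI, so no change can be shown there.
- *That discretion will differ by arm.* The documents do not describe the PI as blinded, but no provision makes the response depend on arm, and silence is not evidence of bias.

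**Conclusion.** The contradiction is real and limited. It concerns a participant who reports suicidality at a baseline or follow-up assessment and is then judged not at risk. For that participant, Risk 2 requires parent notification and a facilitated emergency evaluation, Risk 3 (Assessments) requires neither, and Ongoing Safeguards leaves the evaluation to the PI. This is a conflict between stated rules, not a missing detail, and it should be corrected because it bears on safety and on what families are told.

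Its size cannot be given. The documents state no rate of suicidality reports after enrolment and no proportion of such reports that end in a negative determination. A reader might try to build a count from 14b.2 Risk 5, which mentions "regular suicide risk assessments (~10 participants per study, per month". That rate comes from earlier ED studies, counts risk assessments of any outcome, and may largely reflect screening, so it does not carry over.

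A reader might also infer that serious adverse event counts will shift. Ongoing Safeguards lists attempts, completions and hospitalizations as serious adverse events; reports and evaluations are not listed. Only hospitalizations could vary with the referral rule, and nothing in the documents allows that effect to be estimated. The record review of ED visits and admissions is there to show that such tracking is feasible and is neither the primary nor the secondary exploratory outcome.

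The conclusion assumes that the protocol text governs conduct and that the unseen crisis documents do not already override it.

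**What to change.** Reconcile 14b.1 (Referrals), 14b.2 (Risk 2, Risk 3 Assessments, Ongoing Safeguards and Risk 5) and 14f into a single response pathway for reports of suicidality after enrolment. It should state what happens on the report itself, what happens after the assessment, including when the assessment is negative, and who decides at each step. It should also define or remove the undefined severity term in 14f.

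Check the pathway against the drafted crisis plan and the written reporting protocol so that all three agree. Bring the wording in 14c into line with Eligibility and Enrollment, 14a.1 and 14b.1. Make the confidentiality explanation given to families match the final rule. State that the pathway applies identically in both arms. Which rule is right is for the investigators and the IRB to decide.

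The cost is an IRB amendment to the protocol text and, if needed, to the consent and assent wording. It adds no participants and no procedures.
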